5.3 LIFESTYLE GUIDELINES

5.3.1 CONTRACEPTION

WOMEN OF CHILDBEARING POTENTIAL

Women of childbearing potential (WOCBP) refers to women who are not post-menopausal (defined as 12 months with no menses without an alternative medical cause) or permanently surgically sterile (includes hysterectomy, bilateral salpingectomy, and bilateral oophorectomy).

From Visit 1E until the Termination Visit, sexually active WOCBP must agree to use an acceptable form of contraception. Acceptable forms of contraception are:

1. Intrauterine device (IUD)
2. Implantable rod
3. Established hormonal contraceptive methods. This includes combined (estrogen and progestogen containing) hormonal contraception associated with inhibition of ovulation (oral, intravaginal, or transdermal); progestogen only hormonal contraception associated with inhibition of ovulation (oral, injectable, or implantable). Females who are using hormonal contraceptives must have had consistent use of the same hormonal contraceptive product for at least 4 weeks.

4. Bilateral tubal ligation/occlusion/division
5. Male partner who had a vasectomy provided that the partner is the sole sexual partner of the WOCBP, and that the vasectomized partner has received medical assessment of the success of the surgical procedure or had the vasectomy for at least 6 months

Sexually active WOCBP who withdraw from the study within 30 days after receiving a study injection should remain on an acceptable form of contraception for 30 days after the last study injection.

MEN

For men, no contraception measures are required.

5.4 SCREEN FAILURES

5.4.1 SCREEN FAILURES

Screen failures are defined as participants who consent to participate in the clinical trial but are not subsequently dosed or entered into the study.

5.4.2 SUBJECT RESCREENING

Screen failures are not allowed to rescreen for this study.

5.5 STRATEGIES FOR RECRUITMENT AND RETENTION

A detailed recruitment and retention plan will be maintained by the Sponsor.

5.6 PARTICIPANT WITHDRAWAL OR TERMINATION

5.6.1 REASONS FOR WITHDRAWAL OR TERMINATION

Best efforts will be made to encourage subjects to attend all study visits. Subjects will be informed that they are free to withdraw from the study at any time and for any reason. A discontinuation from the study will occur when a subject who signed informed consent and was dosed ceases participation in this study, regardless of circumstances.

Subjects can be discontinued from the study for one of the following reasons:

- AE
- Total or partial knee replacement of the target knee
- Lost to follow-up after a minimum of 3 attempts have been made to contact the subject, including sending a registered letter
- Withdrawal by subject for reason other than lack of efficacy
- Subject noncompliance
- Physician decision for reason other than lack of efficacy
- Study terminated by Sponsor
- Site terminated by Sponsor

- Request by regulatory authority
- Lack of efficacy
- Pregnancy
- Death
- Other

5.6.2 HANDLING OF PARTICIPANT WITHDRAWALS OR TERMINATION

All Termination Visit procedures and assessments should be performed on subjects who are withdrawn or who voluntarily withdraw, including subjects who withdraw due to partial or total knee replacement. The date the subject is withdrawn from the study and the reason for the discontinuation should be recorded on the electronic case report form (eCRF). The Investigator or designee must complete all applicable eCRFs for subjects who discontinue from the study.

Replacement of subjects who withdraw or discontinue is not allowed.

Total or Partial Knee Replacement Follow-Up

A subject who has had total or partial knee replacement of the target knee should be discontinued from the study. In addition to Termination Visit procedures, sites should make every attempt to follow up with these subjects approximately 6 months after the total or partial knee replacement surgery is completed to assess outcomes of the surgery.

5.7 TERMINATION OR SUSPENSION OF STUDY

The Sponsor reserves the right to terminate the study at any time for administrative or safety reasons. Written notification, documenting the reason for study suspension or termination, will be provided to the Investigator and regulatory authorities as appropriate. If the study is terminated or suspended, the Investigator will promptly inform the Institutional Review Board (IRB) and will provide the reason(s) for the termination or suspension.

6. STUDY AGENT

6.1 STUDY AGENT(S) AND CONTROL DESCRIPTION

6.1.1 ACQUISITION

The Sponsor will be responsible for the manufacturing, labeling, packaging, distribution, and reconciliation of study medication, and ultimate destruction of unused study medication (both LOR drug product and placebo product).

6.1.2 FORMULATION, APPEARANCE, PACKAGING, AND LABELING

LOR drug substance is an off-white powder. LOR drug product is a sterile suspension in diluent containing 0.5% carboxymethylcellulose sodium and 0.05% polysorbate 80 in pH 7.4 phosphate buffered saline. LOR drug and placebo products are supplied as vials of 2.4 mL of formulated suspension. Placebo product contains 0.5% carboxymethylcellulose sodium and 0.05% polysorbate 80 in pH 7.4 phosphate buffered saline.

LOR drug and placebo products will be supplied as single-use vials to the study pharmacist and labeled according to the applicable local and national regulations. For dispensing, dose preparation, and labeling instructions, refer to the Pharmacy Manual.

6.1.3 PRODUCT STORAGE AND STABILITY

LOR drug and placebo products should be stored at the appropriate temperature (15-30 °C [59-86 °F]) and in a restricted area with limited access. Temperature excursions are to be evaluated on a case-by-case basis by the Sponsor.

6.1.4 PREPARATION

At Visit 1E, study medication should be well mixed by the Unblinded Investigator (the drug product is a suspension) before injecting 2 mL intra-articularly into the target knee.

At Visit 3E and for any subsequent injections, study drug preparation and injection do not need to be performed by a designated unblinded individual due to the open-label nature of the remaining portion of the study.

Refer to the Pharmacy Manual for detailed instructions on study injection preparation.

6.1.5 DOSING AND ADMINISTRATION

LOR will be administered in the following dosage strengths:

- 0.07 mg LOR in 2 mL injectable suspension
- 0 mg LOR; 2 mL vehicle-only injection (placebo)

Each subject will maintain the same treatment assignment of LOR or placebo as in the parent study at Visit 1E. At Visit 3E and for any subsequent injections until the Termination Visit, all subjects will receive a LOR injection. Subjects should not have any condition that, in the opinion of the Investigator, constitutes a risk or contraindication for the injections.

At Visit 1E, the injectable drug product or placebo product is to be administered by the Unblinded Investigator as a single injection into the target knee joint. Before administration of the IA knee injection, the subject should be blinded to observation of the study medication and injection procedure according to the processes specified in the Site-Specific Blinding Plan. The Unblinded Investigator must minimize any contact with the subject aside from the injections and may not perform any study assessments throughout the duration of the study. All other subject contact is limited to the Blinded Investigator and other appropriate blinded study personnel. The Unblinded Investigator does not need to be the same person for the duration of the study. At Visit 3E and for any subsequent injections, the LOR injections do not need to be performed by a designated Unblinded Investigator due to the open-label nature of the remaining portion of the study.

Only 1 knee will be treated for each subject in this study. The injection can be done either through lateral or medial (including superior/suprapatellar, midpatellar, and inferior/anterior) approaches, based on the standard practice of the Unblinded Investigator/injector or the knee examination of the subject. Although not required, the injection may be guided by ultrasound or

fluoroscopy without contrast if it is the standard practice of the Unblinded Investigator/injector. Only topical anesthetics are allowed before the study injection. Local anesthetic injections are prohibited.

The Unblinded Investigator/injector should place the needle into the joint and the total volume contained in the syringe is to be injected into the joint space. Because LOR drug product is a suspension, prior aspiration of synovial fluid into the syringe containing the injectate should be avoided to prevent trapping of particles within synovial aspirate/cellular content residues. Aspiration of joint fluid into a separate empty syringe is allowed if it is the standard practice of the injector to confirm correct needle placement. For subjects with moderate to large effusion in the target knee, aspiration of the effusion prior to injection of study medication is recommended. The study medication should then subsequently be injected via syringe exchange. The approximate volume of fluid aspirated should be recorded in the eCRF.

The Sponsor will provide sterile needles and syringes that should be used for the study injections.

6.1.6 ROUTE OF ADMINISTRATION

Injectable LOR drug product or placebo product is to be administered as an IA injection into the target knee joint.

6.1.7 STARTING DOSE AND DOSE ESCALATION SCHEDULE

Not applicable to this study.

6.1.8 DOSE ADJUSTMENTS/MODIFICATIONS/DELAYS

No modification in the specified dose concentration or volume (2 mL) of the study injection will be allowed.

6.1.9 DURATION OF THERAPY

Injectable LOR drug product or placebo product is to be administered as a single IA injection into the target knee joint at Visit 1E. LOR is to be administered as an IA injection in the target knee joint every 52 weeks starting at Visit 3E until the Termination Visit.

6.1.10 STUDY INTERVENTION COMPLIANCE

Not applicable to this study.

6.1.11 DEVICE SPECIFIC CONSIDERATIONS

Not applicable to this study.

6.2 STUDY AGENT ACCOUNTABILITY PROCEDURES

The study medications supplied for this study are for use only in subjects properly consented and

enrolled into this protocol.

All used and unused vials of LOR drug and placebo products received must be returned and accounted for. All injections prepared and dispensed must also be logged. The log includes, but is not limited to, the following:

- Subject number and initials
- Date that study medication was injected
- Quantity dispensed (drug product vials and placebo vials)
- Quantity returned/used (drug product vials and placebo vials)

All study medication dispensed by the Unblinded Investigator and/or unblinded designee will be inventoried and accounted for throughout the study until all subjects at each site complete Visit 3E. The Unblinded Investigator and/or unblinded designee must maintain an accurate, up-to-date dispensing log for all study medications supplied by the Sponsor. Study medication dispensed for all subjects must be recorded on the drug accountability forms. The study medication dispensing log and remaining drug inventory will be reviewed by the Sponsor-designated unblinded clinical monitor.

Starting at Visit 3E and for subsequent injections, subjects will receive open-labeled IP. Accountability will be documented on a new, separate accountability log with the same information as noted above. The open-labeled IP and the separate IP accountability log will be reviewed, and dosing will be verified by a Sponsor-designated clinical monitor (not the unblinded clinical monitor).

For the Visit 1E injections, used and unused study medications must be kept in a secure, blinded location physically separated from standard clinic or office drug supplies, and with access limited to the Unblinded Investigator and/or unblinded designee. Once all subjects at a site have had their Visit 1E injection, IP will be accounted for by the unblinded clinical monitor, and the IP can be returned to the depot. Procedures for return or destruction of used and unused vials of the study medication will be provided in the Pharmacy Manual. Open-labeled IP to be used for Visit 3E and subsequent injections will need to be kept in a secure, temperature-controlled location separate from the blinded IP. Accountability for the initial blinded IP will be separate from the open-label IP and sites will need to maintain separate accountability records and pharmacy binders until all subjects at the site are receiving the open-labeled IP, the blind has been lifted, and the parent-study (SM04690-OA-11) database has been locked.

7. STUDY PROCEDURES AND SCHEDULE

7.1 STUDY PROCEDURES/EVALUATIONS

7.1.1 STUDY SPECIFIC PROCEDURES

Collection of Adverse Events Data

Data regarding AEs will be collected in this study. As this is an extension trial, AE collection will continue from the parent study, ongoing AEs at the end of the parent study will continue to be monitored, and new AEs that occur during this study will be recorded. Changes to ongoing

AEs that occur after the parent-study EOS visit will not be recorded in the parent study. AEs will be assessed through the Termination Visit.

Each subject will be observed and queried by the Investigator or designee at each study visit for any continuing AEs or new AEs since the previous visit. The subject may be asked to return to the site for an unscheduled visit if an AE occurs between study visits, and if, in the opinion of the Investigator, the AE requires a study visit for full evaluation. The following information will be recorded within the eCRF for each AE: Description of the event, date of onset and resolution, and severity as assessed by the Investigator according to the Clinical Data Interchange Standards Consortium (CDISC) Severity/Intensity Scale for Adverse Events (AESEV) ([Table 1](#)), causal relationship to study medication, outcome, and any action taken.

In this protocol, signs and symptoms of exacerbation or worsening of target knee OA will be captured in the context of efficacy assessments and recorded on specific pages of the eCRF. Anticipated fluctuations or anticipated deterioration (in the opinion of the Investigator) of the underlying disease (target knee OA) will not be considered as AEs nor captured on the AE eCRF.

Whenever possible, it is preferable to record a diagnosis as the AE term rather than a series of symptoms relating to a diagnosis. Fluctuations of pre-existing conditions that do not represent a clinically significant exacerbation or worsening need not be considered AEs.

AEs will be followed until the subject's last visit or resolution, whichever comes first. For subjects who discontinue from the study within 30 days of their study injection, AEs that are ongoing at the subject's last visit will be followed for 30 days after administration of the last dose or until resolution, whichever comes first. Resolution is defined as the return to baseline status or stabilization of the condition. SAEs and selected AEs identified by the Investigator or the Sponsor to warrant further follow-up that are ongoing at a subject's last visit will be followed until resolution.

Medical History

A follow-up on Medical History (collected in the parent study) will be performed at the Termination Visit to capture End Dates of any ongoing medical history.

Physical Examination

A general physical examination will be conducted at Visit 3E and the Termination Visit. Results of the physical examination will be noted in the source documents. Any clinically significant finding should be reported as an AE.

Knee Examination

A knee examination of both knees will be conducted at all clinic visits after Visit 1E. Results of the knee examination will be noted in the source documents. Any clinically significant finding should be reported as an AE.

Weight

Weight measurements will be taken at Visit 2E, Visit 3E, every 52 weeks thereafter (e.g., Visits 6E, 8E, etc.), and at the Termination Visit.

Vital Signs

Vital signs will be measured by a qualified staff member at Visit 2E, Visit 3E, every 52 weeks thereafter (e.g., Visits 6E, 8E, etc.), and at the Termination Visit.

At each time point, the following vital signs will be measured:

- Pulse rate
- Blood pressure (systolic and diastolic) after the subject rests (sitting or supine) for at least 5 minutes

At visits when the subject will receive an IA injection (e.g., Visits 3E, 6E, 8E, etc.), temperature will also be measured.

Any measurement that is, in the opinion of the Investigator, abnormal AND clinically significant must be recorded as an AE.

Radiograph of Knee Joints

Radiograph of the knee joints will be taken at all clinic visits after Visit 1E.

Detailed instructions for obtaining and managing the radiographs will be provided to the investigational center before subject enrollment. As described in the Image Review Charter – Image Acquisition Guidelines, radiographs should be obtained in the posterior-anterior (PA) view.

Upon receipt of images, the central imaging vendor will assess the image quality as acceptable or unacceptable. It is recommended that the Investigator attempt up to 3 additional image captures in order to obtain an acceptable image.

All radiographs will be submitted to an independent radiologist at the central imaging vendor who will document mJSW. The central imaging vendor does not provide medical advice, clinical diagnosis, or treatment recommendations. These imaging assessments and quantitative measurements provided to the Sponsor do not and shall not constitute a medical diagnosis, treatment recommendation, or medical advice, and are not intended to be used as a substitute for the study Investigator's or other qualified health care professional's medical diagnosis, treatment, or advice. If any unusual pathology is noted in the study images, the Sponsor will be notified of the finding and will promptly notify the Investigator. The Investigator will then assess the clinical significance as well as any follow-up procedures that need to be completed.

Pain Numeric Rating Scale

The pain NRS is an 11-point scale [0-10] for subject self-reporting of average knee pain in the last 24 hours. The NRS will be anchored by descriptors at each end ("No Pain" on the left and "Pain as bad as you can imagine" on the right). A pain NRS assessment will be completed by the subjects at all clinic visits.

Pain NRS questionnaires will be provided by the Sponsor. Upon completion of the pain NRS, subjects will sign or initial, then date the source document to indicate that the assessment is reported accurately.

Western Ontario and McMaster Universities Arthritis Index

The WOMAC is a widely used, proprietary outcome measurement tool used by health professionals to evaluate the condition of patients with OA of the knee and hip, including pain, stiffness, and physical functioning of a target joint. The WOMAC Version NRS 3.1 questionnaire will be completed by the subject for their target knee at all clinic visits after Visit 1E.

WOMAC questionnaires will be provided by the Sponsor and may not be reproduced. Upon completion of the WOMAC, subjects will sign or initial, then date the source document to indicate that the assessment is reported accurately.

Patient Acceptable Symptom State Questionnaire

At Visit 1E, Visit 3E, every 52 weeks thereafter (e.g., Visits 6E, 8E, etc.), and at the Termination Visit, subjects will be asked the following, using a paper questionnaire: “Taking into account all the activities you have during your daily life, your level of pain, and also your functional impairment, do you consider that your current state is satisfactory?” Subjects are able to choose the answers of “Yes” or “No.”

PASS questionnaires will be provided by the Sponsor. Upon completion of the questionnaire, subjects will sign or initial, then date the source document to indicate that the assessment is reported accurately.

36-Item Short Form Health Survey

The SF-36 is a widely used questionnaire that relies upon subject self-reporting to measure the subject’s health-related quality of life. The SF-36 will be completed by the subject at Visit 3E, every 52 weeks thereafter (e.g., Visits 6E, 8E, etc.), and at the Termination Visit.

The SF-36 is a paper questionnaire that will be provided by the Sponsor and may not be reproduced. Upon completion of the SF-36, the subject will sign or initial, then date the source document to indicate that the quality of life assessment is reported accurately.

Assessment of NSAID/Acetaminophen Usage

Information about NSAID and acetaminophen usage will be collected at all clinic visits after Visit 1E. Subjects will be asked to recall the name, indication, route of administration, usual total daily dose, and usual number of days taken per week of any NSAID or acetaminophen medications during the previous 4 weeks. Assessment of NSAID/acetaminophen usage will be documented on the “NSAID/Acetaminophen Usage” eCRF.

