8.3 TIME PERIOD AND FREQUENCY FOR EVENT ASSESSMENT AND FOLLOW-UP

The reporting period for AEs starts immediately following the parent-study EOS visit and ends after the final study visit.

AEs will be followed until the subject's last visit or resolution, whichever comes first. For subjects who discontinue from the study within 30 days of their last study injection, AEs that are ongoing at the subject's last visit will be followed for 30 days after administration of the last dose or until resolution, whichever comes first. Resolution is defined as the return to baseline status or stabilization of the condition. SAEs and selected AEs identified by the Investigator or the Sponsor to warrant further follow-up that are ongoing at a subject's last visit will be followed until resolution.

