4.1 Changes to Overall Study Design and Plan

The sponsor elected to administratively terminate this study. All active subjects were requested to continue the study until they completed Visit 6E (Week 100); subjects injected at this visit were followed-up via phone call 10 days (+/-3 days) for safety data collection. Subjects that had already completed their Visit 6E (Week 100) were asked to schedule a termination visit as soon as possible. All procedures for the termination visit should be performed; however, as provided in the protocol, an additional X-ray was not required if a subject had an X-ray taken within the 12 weeks prior to their termination visit.

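### New adverse events starting after an early exit, but within 30 days of an injection, are picked up by no required contact, because the 30-day rule covers only events already ongoing at the last visit

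*Protocol*

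**What the plan says.** Three protocol rules decide which AEs are collected near the end of a subject's participation.

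- **How new events are found.** Under Protocol 7.1.1, subjects are "queried by the Investigator or designee at each study visit for any continuing AEs or new AEs since the previous visit".
- **When collection stops.** Protocol 7.1.1: "AEs will be assessed through the Termination Visit". Protocol 8.3: "The reporting period for AEs starts immediately following the parent-study EOS visit and ends after the final study visit".
- **What is extended past the last visit.** The rule in Protocol 7.1.1 opens "For subjects who discontinue from the study within 30 days of their study injection, AEs that are ongoing", and its main clause reads "AEs that are ongoing at the subject's last visit will be followed for 30 days after administration of the last dose or until resolution". Protocol 8.3 has the same limit: "For subjects who discontinue from the study within 30 days of their last study injection, AEs that are ongoing at the subject's last visit". The longer follow-up for SAEs and selected AEs in both sections is also confined to events ongoing at the last visit.

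Protocol 8.4.2 requires SAEs to be reported within 24 hours of the site learning of them and states no end date of its own.

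On the analysis side, SAP 10.1 tabulates AEs in three periods separated by the OA-07 injections, the last running from the third injection to EOS. SAP 4.1 describes the administrative termination: active subjects continued to Visit 6E, and "subjects injected at this visit were followed-up via phone call 10 days (+/-3 days) for safety data collection".

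**The concern.** The protocol already uses 30 days after an injection as a safety horizon. Events present at exit are followed to that point, and Protocol 5.3.1 says that women of childbearing potential who withdraw early "should remain on an acceptable form of contraception for 30 days after the last study injection". New events are treated differently. An event that starts on Day 4 and is ongoing at a Day 5 final visit is followed to Day 30. An event that starts on Day 6 in the same subject is asked about by no one.

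AE and SAE incidence is a listed safety endpoint. Protocol 2.3.3 notes that no completed study had examined repeated LOR injections when the protocol was written. Delayed injection-site or joint reactions could fall in these weeks. For subjects whose third OA-07 injection was at Visit 6E under the termination, the third AE period in SAP 10.1 may rest on only one to two weeks of observation. The planned output is numbers and percentages of subjects, and the only exposure output (SAP 12.2) is a subject-level listing. A reader of the table could not tell how short that observation was.

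**Working it through.** The documents state no figure on this point, so there is none to reproduce. The check is a comparison of the rules, followed by day arithmetic.

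**1. Who is asked about new AEs, and until when**

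| Situation | Query for new AEs after the last injection | Reaches Day 30? |
|---|---|---|
| Stays in the study | At every later visit, back to the previous visit (7.1.1) | Yes |
| Has the Visit 3E injection and stays | Also a call at Week 52, nominally 4 weeks later (7.3.2) | Nominally Day 28, then later visits |
| Exits within 30 days of any injection | Termination Visit only; no minimum interval from the injection (5.6.2, 7.3.3) | No |
| Active at termination and injected at Visit 6E | Call at 10 ± 3 days (SAP 4.1) | No |
| Already past Visit 6E at termination | Termination visit as soon as possible (SAP 4.1) | Depends on timing; may be after Day 30 |

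**2. Days not queried**

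Input: d = day of last contact after the last injection. Days not queried = 30 − d; share = (30 − d)/30.

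- d = 1: 29 days, 97%
- d = 7: 23 days, 77%
- d = 10: 20 days, 67%
- d = 13: 17 days, 57%
- d = 20: 10 days, 33%
- d = 29: 1 day, 3%

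The call at 10 ± 3 days gives d = 7 to 13, so 17 to 23 days are not queried.

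**3. Share of 30-day new-onset events outside the queried days**

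The onset pattern is an assumption; the documents give none. With uniform onset the share equals the day share in step 2. With exponentially declining onset of half-life h days:

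share = (2^(−d/h) − 2^(−30/h)) / (1 − 2^(−30/h))

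| Onset pattern (assumed) | d = 7 | d = 10 | d = 13 |
|---|---|---|---|
| Uniform | 77% | 67% | 57% |
| Half-life 14 days | 62% | 50% | 39% |
| Half-life 7 days | 47% | 34% | 24% |

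Example, h = 7 and d = 7: 2^(−1) = 0.500 and 2^(−30/7) = 0.051, so (0.500 − 0.051)/(1 − 0.051) = 0.47.

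**4. Rough count from ordinary early exits**

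Assumed inputs apart from the approximate enrolment of 500: 1% to 5% exit within 30 days of an injection, 5% to 20% have a new AE in 30 days, and 25% to 90% of the window is not queried.

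- Low end: 500 × 0.01 × 0.05 × 0.25 = 0.06
- High end: 500 × 0.05 × 0.20 × 0.90 = 4.5

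That is about 0.1 to 4.5 subjects with an event that no required contact would find. No comparable count can be given for Visit 6E, because the number injected there under the termination is not stated.

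**The case against.** The strongest reply is that the weight of the point depends on readings the documents do not support. Much of that is right.

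- **That late events are never counted.** A reader might infer this from the reporting period and the EOS cut-off. No section says an event volunteered to the site after the last visit must be discarded, 8.4.2 ties SAE reporting to site knowledge with no end date, and the SAP does not define EOS as the last clinic visit. What is established is that nobody is required to ask.
- **That every subject injected at Visit 6E was last contacted on Day 7 to 13.** SAP 4.1 separates active subjects from those who had already completed Visit 6E. The second group's termination visit may fall well after Day 30, so the affected group cannot be called large.
- **That the Visit 6E cases distort the placebo-controlled AE endpoint.** SAP 3.2.3 limits that endpoint to the time before the second OA-07 injection. For subjects on schedule, Visit 6E is the third, in the open-label part.
- **That unobserved days are analysed as event-free.** SAP 10.1 plans counts and percentages by period, with no 30-day risk and no person-time rate. The danger lies in how a percentage is read.
- **That 30 days is a declared onset window.** It is not. The protocol uses it for follow-up of existing events and for contraception. Applying it to new onsets is a consistency argument.

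It is also fair to say that the SAP, signed in November 2023, describes the Visit 6E calls in the past tense, and changing a cut-off recovers no data that were not collected. None of this supplies a required query for new events after an early exit.

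**Conclusion.** The point holds in a limited form. It rests on the wording of Protocol 7.1.1 and 8.3, which is explicit, and on the absence of any other required contact.

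- **Placebo-controlled AE endpoint (SAP 3.2.3).** The gap mainly concerns exits within 30 days of Visit 1E. The effect is probably small. The illustration of about 0.1 to 4.5 subjects in 500 covers ordinary early exits after any injection and depends on assumed exit and event rates.
- **Third AE period in SAP 10.1.** For active subjects injected at Visit 6E whose last planned contact was the phone call, 17 to 23 of 30 days (57% to 77%) are not queried. The share of 30-day onsets falling there runs from 24% to 77% over the assumed onset patterns. This period is descriptive and uncontrolled, so the risk is that its percentages are read as full post-injection risk.

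The number of subjects in each group is not given, and the conclusion does not depend on it.

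**What to change.** **Protocol 7.1.1 and 8.3.** End the AE/SAE reporting period, for new as well as ongoing events, at the later of the final study visit and 30 days after the last study injection. This is the horizon the protocol already applies to ongoing events. Add one phone contact for consenting subjects whose last contact would be earlier. Reconcile 8.4.2 with this, so that the end of SAE reporting is the same in both places.

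**SAP 10.1.** Close the last AE period at that same date, and say what EOS means where it is used. For each period and treatment group, report the length of post-injection observation (last contact date minus injection date), with the AE percentages read against it. Where calls can no longer be made, this step still applies and needs only dates that should already be held.

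**Cost.** Wording in two documents, one extra call for the subjects concerned, and one summary table. Subjects who withdraw consent cannot be called, so some of the gap stays. Reported AE counts may rise slightly.
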